This project follows a systematic approach to the development and evaluation of the FMF Connect mHealth intervention. The app is designed for use by caregivers, utilizes a cloud-based infrastructure, and builds on our existing open source framework for the development of medical apps [11], and those of others [12,13]. Feasibility tests and iterative feedback from diverse caregivers have aided in fine tuning caregiver instructions, content, and user-interface features throughout the development process.

The proposed RCT will establish the efficacy of the FMF Connect mHealth intervention in a large-scale efficacy trial. It will also assess the patterns of app usage that relate to the greatest improvements in child and caregiver outcomes and test whether text-based coaching increases engagement with the app. Consistent with prior FMF trials, targeted outcomes include satisfaction, child behavior problems, caregiver FASD/advocacy knowledge, attributions of misbehavior, parenting practices, parenting efficacy, self-care, and social support. This novel mHealth intervention has the potential to reach many families in need and reduce significant barriers to care, resulting in broader public health impact.

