Upon completion of the consent survey, a static copy of their responses in the form of a consent-specific PDF will be stored in the project's File Repository in REDCap (to allow for versioning). The e-Consent Framework in REDCap also records the IP address of the participant and displays this information in the file repository in order to help regulate potential duplicate forms from a single IP address. A PDF file of the completed consent form will be available for download by the user. The PDF can also be emailed to participants or printed/sent to participants in the mail on request if they are unable to open or save a copy electronically on their device.

After completing the consent document, participants will be directed in REDCap to answer screening questions to assess eligibility for the study (see Screening Form). If eligibility criteria clearly aren't met (e.g., out of age range, outside the US, no smartphone, etc), parents/caregivers will be informed immediately that they aren't eligible and the module will end. For parents/caregivers who appear to meet criteria or in cases where parents/caregivers answer "unsure" for any of the questions, contact information will then be gathered. Contact information will also include necessary variables to generate their "globally unique identifier" (GUID), which is used in other CIFASD studies (<https://nda.nih.gov/s/guid/nda-guid.html>).

Common variables are used across several CIFASD studies. We have adapted and streamlined several CIFASD Common Forms for the purposes of this study, which will be administered next in REDCap. These forms include: the Parent Demographic Form, the Child Demographic Form, the Prenatal Exposure History, and the FASD Diagnosis History forms. These forms take about 15 minutes or less to complete in total. After completing the Consenting and Screening module, participants will be notified that project staff will review all submitted information to assess final eligibility.

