9. STUDY PROCEDURES

Data Collection & Randomization Procedures

Parents/caregivers who are eligible for the study will be sent an email inviting them to complete the baseline study surveys (see survey battery below) administered by REDCap. Participants will be

asked to enter their zip code to verify their identity when completing baseline and follow-up surveys (this will be verified against value entered in demographic surveys in the screening module). Families deemed ineligible after detailed review will be informed of their status.

Following baseline survey completion, participants will be randomized to one of three arms of the RCT:

1. FMF Connect app + text based coaching (within the app)
2. FMF Connect app (without coaching)
3. Waitlist control

Randomization will occur through the REDCap Randomization module, with an equal allocation pattern across groups. Participants will be notified of their group status via email. Emails for parents/caregivers in either of the FMF Connect app intervention groups (groups 1 and 2) will also include instructions of how to install the FMF Connect app on their devices. The email for the parents/caregivers in the FMF Connect app + coaching group (group 1) will inform them that they will receive an introductory email from their assigned coach in the next few days. Details about the FMF Connect app and Coaching interventions and described below.

All participants regardless of group assignment will receive emails through REDCap at 6 weeks and 12 weeks inviting them to complete follow-up surveys, along with a personalized link (see survey battery below). The assessment battery is estimated to take 35-45 minutes to complete at T1 and T3; T2 is estimated at 15-20 min. Waitlist control participants will receive the FMF Connect app following T3 survey completion.

Measure	Baseline (T1)	6-Weeks (T2)	12-Weeks (T3)
Eyberg Child Behavior Inventory (5-8min)	X		X
Reasons for Children’s Behavior Scale (4-6min)	X	X	X
Everyday Life Scale (4-6min)	X	X	X
Parenting Sense of Competence Scale (3-5min)	X	X	X
Family Needs Questionnaire (3-5min)	X		X
Knowledge & Advocacy Questionnaire (15-20min)	X		X
Self-Care and Support Assessment (3-5min)	X		X
Adverse Childhood Experiences (2 min)	X		
Family Background & Services Survey (5-10min)	X		X
COVID-19 Experiences Survey (5 min)			X
User Version of the Mobile Health Application Rating Scale (5-8min)			X

FMF Connect mHealth Intervention

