19. DATA ANALYSIS PLAN

Aim 1: For the two intervention groups, compare patterns of app usage (i.e., frequency, duration, use of core components) that relate to greater improvements in child and caregiver outcomes. Assess whether FMF Connect + Coaching results in higher usage of the app relative to FMF Connect alone.

A series of Multiple Regression analyses will test how app usage (i.e., frequency, duration, content/components accessed) relates to change in outcomes (i.e., parenting efficacy, FASD knowledge, family needs, child behavior) over time, controlling for pre-intervention level of functioning. With a sample size of 100 (n=50 per intervention group) and assuming $\alpha = .05$, there will be power .80 to detect small/medium effects ($f^2=.10$), .94 to detect medium effects ($f^2=.15$), and power $> .99$ to detect large effects ($f^2=.35$).

Aim 2: Examine whether families randomized to the three study arms differ in outcomes.

Repeated Measures Analysis of Variance will test whether families randomized to FMF Connect groups demonstrate improved outcomes relative to the waitlist group at 12 weeks. Pairwise comparisons will test for differences among intervention groups to determine if coaching adds additional benefit. Assuming a correlation among repeated measures ranging from .3 to .5 ($\alpha = .05$), with a sample of 150 and 3 time points, there will be power between .87-.96 to detect a small/medium effect ($f=.175$) and $>.99$ to detect medium and large effects ($f=.25$ and $f=.40$).

Aim 3: Examine whether parental attributions of child misbehavior mediate intervention-related changes in parenting efficacy and child behavior.

Mediation analyses will test whether parental attribution mediates the effects of FMF Connect on parenting efficacy and child behavior, including baseline levels of the respective outcomes. Given a sample size of 150, there will be adequate power ($>.80$) to detect small/medium effects within the mediation models using the bias-corrected bootstrap method.

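### Aim 1 relates self-chosen app usage to outcome change with adjustment only for pre-intervention level; add a pre-specified model with randomised arm and a few baseline covariates already collected, and report both results as associations.

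*Combined protocol and SAP*

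**What the plan says.** The background (section 2) says the trial will "assess the patterns of app usage that relate to the greatest improvements in child and caregiver outcomes". Section 19, Aim 1, carries this out: "A series of Multiple Regression analyses will test how app usage" relates to change in parenting efficacy, knowledge, family needs and child behaviour, "controlling for pre-intervention level of functioning". No other covariate is named. The analysis set is the two app arms together, 100 participants with 50 per arm.

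Section 14 leaves the amount of use, including none, to the participant. Section 5 expects about 80% of families who complete baseline to install the app and use it at least once.

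Section 8 collects "the Parent Demographic Form, the Child Demographic Form, the Prenatal Exposure History, and the FASD Diagnosis History forms" at screening. The survey table in section 9 adds adverse childhood experiences and a family background and services survey at T1. Randomisation follows completion of the baseline surveys, so all of these precede it. Section 19 uses none of them in Aim 1. It also does not put randomised arm in these regressions, although sections 1 and 9 expect coaching to raise usage.

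**The concern.** Within the app arms, heavy and light users differ by their own choice as well as by coaching. Section 2 itself names money, childcare and stigma as barriers to care, so it is plausible that circumstances affecting how much a caregiver uses the app also affect how the family changes over 12 weeks. Adjusting for the starting level of an outcome removes confounding that runs through that level. It does not remove the influence of factors acting on later change.

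Arm raises a related problem. If coaching raises usage and also helps families directly, a pooled usage coefficient without arm absorbs part of the coaching effect.

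What is at stake is how the usage results are read: a usage pattern could be reported as going with the greatest improvement when it partly marks family circumstances or coaching.

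**Working it through.** **1. The plan's own power figures.** Inputs from section 19: N = 100, α = .05, f² = .10, .15 and .35, with stated power .80, .94 and above .99. For a test of u predictors in a model with k terms, the noncentrality is λ = f²·N, with u and N − k − 1 degrees of freedom. With u = 2 and k = 3, power is .802, .937 and .9998, which matches. With u = 1 it is .879 and .970 at the two smaller effects; with u = 3 it is .742 and .905. The stated power therefore reproduces with two tested predictors and is not at fault. The issue is bias.

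**2. What an omitted factor does.** Suppose usage has no true effect. Let a factor have correlation a with usage and partial correlation b with the follow-up outcome given baseline. Leaving it out produces a spurious partial correlation r = a·b. For independent factors these products add, with their signs. Then f² = r²/(1 − r²) and λ = 100·f², and the rejection rate comes from the noncentral F with 1 and 97 degrees of freedom. The documents give no values for a or b, so these are assumptions. The simulated column used 5,000 trials per setting and a baseline-outcome correlation of .5.

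| a = b | Factors, same direction | r | λ | Rejection, formula | Rejection, simulated |
|---|---|---|---|---|---|
| .2 | 1 | .04 | 0.16 | 7% | 7% |
| .2 | 2 | .08 | 0.64 | 12% | 13% |
| .2 | 3 | .12 | 1.46 | 22% | 23% |
| .3 | 1 | .09 | 0.82 | 15% | 14% |
| .3 | 2 | .18 | 3.35 | 44% | 42% |
| .3 | 3 | .27 | 7.86 | 79% | 77% |

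As an example of the steps, for one factor at .3: r = .3 × .3 = .09, f² = .0081/.9919 = .0082, and λ = 0.82.

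**3. Dependence on direction.** With three factors at .3 and one reversed, r = .09 + .09 − .09 = .09, and simulation gives 14%. With two opposed factors, r = 0 and the rate is 5%. Three aligned factors at only .1 give 6%. In the 77% case the omitted factors together explain 3 × .09 = 27% of both usage and the residual outcome.

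**4. What adjustment recovers.** If the exact factors are added, simulated rejection returns to about 5% in every setting. If only proxies with an assumed reliability of .5 are added, one factor at .3 still gives about 8% and three aligned factors at .3 give 33%.

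**5. Cost of adjustment.** Four caregiver types take 3 degrees of freedom. One socioeconomic item, the adverse-experiences score, T1 services and one child variable take 1 each. The sum is 3 + 1 + 1 + 1 + 1 = 7, or 8 with arm. With two tested predictors and 8 added terms, power is .801 at f² = .10 and .936 at f² = .15, so the degrees of freedom cost almost nothing. If the covariates explain a share R² of usage, the effective f² is f²·(1 − R²). For assumed R² of .10, .20 and .30, power at f² = .10 is about .76, .70 and .64, and at f² = .15 about .91, .87 and .82. These figures take no credit for outcome variance that the covariates explain.

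**The case against.** The strongest reply is that Aim 1 is worded as association: usage is said to relate to change, and no section calls these regressions a causal effect. Efficacy rests on the randomised Aim 2 comparison. This stands. A reader might infer from the point that the Aim 1 test is invalid, or that its coefficients will be used to redesign the app; the documents support neither. Section 14 mentions improving the app, but from survey data and user feedback. What remains is a risk of misreading, and the plan says nothing to limit it.

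Second, the larger rejection rates need every omitted factor to push the same way. Opposing signs are plausible: families under more strain might use the app more and improve less. This also stands. It leaves the direction of the bias unknown; it does not show that the bias is absent.

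Third, the collected variables are proxies, and no baseline measure of motivation is listed. A reader might infer that adding covariates restores a 5% error rate. It does so only if the true confounders are measured without error, which cannot be assumed here.

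Fourth, pre-intervention level of functioning is not defined and could be meant more broadly. Aim 3 speaks of baseline levels of the respective outcomes, and the baseline outcome is the natural reading here too. If a wider set was intended, section 19 needs to list it.

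**Conclusion.** The point holds as an incomplete adjustment set in an observational analysis. Usage is largely self-chosen, the only stated adjustment is for pre-intervention level, and measured circumstances that could drive both usage and improvement are left in the usage coefficient, as is randomised arm.

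The magnitude is illustrative. Under assumed same-direction correlations of .2 to .3, the nominal 5% test rejects about 7% to 14% of the time with one omitted factor and 23% to 77% with three, and opposing factors can bring it back to 5%. The 77% is the top of an assumed range and should not be read as an expected error rate for this trial. The documents do not support a claim that the adjusted analysis would isolate the effect of usage.

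The randomised Aim 2 comparison and the randomised comparison of usage with and without coaching are not affected.

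**What to change.** In section 19, Aim 1, keep the stated model and add a pre-specified adjusted model to every usage-outcome regression. It should contain:

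- randomised arm (coaching or not);
- caregiver type (biological, foster, adoptive, kin);
- one socioeconomic item, if the Parent Demographic Form has one (its items are not in the documents);
- the adverse childhood experiences score;
- services at T1;
- child age or diagnosis status, whichever is chosen in advance.

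Define pre-intervention level of functioning in the same place. Report the usage coefficient from both models as an association, and state that unmeasured motivation and imperfect proxies leave residual confounding.

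This takes a few sentences, with no new data and no added participant burden. It uses about 7 to 8 degrees of freedom of 100. Any material loss of power comes from overlap between covariates and usage: from .80 to about .76 to .64 at f² = .10 if they explain an assumed 10% to 30% of it. Fixing the set now also prevents covariates being chosen after the results are seen.

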1. PURPOSE OF STUDY

This study represents the third phase of a larger research project developed for a U01 award as part of the Collaborative Initiative on Fetal Alcohol Spectrum Disorders (CIFASD) funded by the National Institute on Alcohol Abuse and Alcoholism (NIAAA). The overall project aims to develop and evaluate a mobile health (mHealth) application (app) for parents/caregivers of children with fetal alcohol spectrum disorders (FASD). The primary focus of the FMF Connect app is to provide parent/caregiver education and support.

The first phase of this project was approved under IRB protocol #1266 (legacy RSRB#67394). In that phase we used qualitative research methods to engage parents and caregivers in the development of the mHealth intervention and obtain iterative feedback on acceptability and feasibility. A prototype of the app was developed in both iOS and Android and beta-testing was completed with parents/caregivers and providers. In the second phase of the study, we conducted a feasibility trial of the FMF Connect app with parents/caregivers under IRB protocol #4433. This included quantitative pre-post surveys and qualitative interviews with a subsample of users to optimize the intervention and trial procedures. In this third phase, we will conduct a larger scale randomized controlled trial (RCT) to test the efficacy of the FMF Connect app for parents/caregivers of children with FASD. We hypothesize that participants who receive the FMF Connect app (with or without the additional Coaching Module) will have improve outcomes relative to the waitlist control group. We anticipate the Coaching Module will increase participant engagement and usage of the FMF Connect app. Finally, we hypothesize that parental attributions of behavior targeted by the FMF Connect app will mediate intervention effects on child behavior and parenting self-efficacy.

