4. STUDY DESIGN

This study involves a three arm RCT with equal allocation to the following conditions: (1) FMF Connect + coaching, (2) FMF Connect alone, and (3) waitlist control. Quantitative survey data will be collected at three timepoints: baseline (T1), 6-weeks (T2), and 12-weeks (T3). The T2 timepoint will involve an abbreviated battery designed to allow statistical tests of mediation hypotheses (see Data Analysis Plan below). Primary study outcomes include child behavior, parent FASD knowledge,

parenting self-efficacy, behavior attributions, family needs met, and parent use of self-care. We are also interested in participant ratings of app quality and patterns of app usage. App usage will be recorded through AWS during the study period. After T3, study participants in the waitlist control group will receive the FMF Connect app.

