14. SUBJECT WITHDRAWALS

Subjects will be advised during the consent process that they have the right to withdraw from the study at any time without prejudice. They can choose to use the app as much as they want (or not at all). We are interested in obtaining survey data as well as feedback about the user experience from as many participants as possible, including those who chose not to use the app or found it hard to

navigate. This information is useful in identifying ways to improve the app and facilitate user engagement. Subjects can choose not to complete any or all of the study assessments. They can also completely withdraw from the study with no future contact if they choose. In this case, any data they have previously provided may be used in analyses.

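### Aim 2 compares the randomised arms by repeated-measures ANOVA without baseline as a covariate; adjusting the 12-week score for T1 would be more precise at almost no cost

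*Combined protocol and SAP*

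**What the plan says.** Section 19, Aim 2, specifies: "Repeated Measures Analysis of Variance will test whether families randomized to FMF Connect groups demonstrate improved outcomes relative to the waitlist group at 12 weeks". Whether coaching adds benefit is left to comparisons between pairs of arms. No covariate is named, and the plan does not say which ANOVA term (group, time or their interaction) is tested. The power statement uses 150 participants, three time points, α = .05 and f = .175, "Assuming a correlation among repeated measures ranging from .3 to .5", and gives power of .87 to .96.

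The other two aims in section 19 do adjust for baseline. Aim 1 is analysed "controlling for pre-intervention level of functioning" and Aim 3 "including baseline levels of the respective outcomes".

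Section 9 places randomisation after completion of the baseline surveys, so T1 is a proper pre-randomisation covariate. Section 4 says: "The T2 timepoint will involve an abbreviated battery designed to allow statistical tests of mediation hypotheses". In the section 9 schedule, the Eyberg inventory and the family needs, knowledge and self-care scales appear at T1 and T3 only. The attributions, Everyday Life and parenting competence scales also appear at T2.

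**The concern.** Repeated-measures ANOVA does use T1, but as one of the outcome levels. With two visits, the group-by-time test then rests on T3 minus T1, which fixes the slope on baseline at 1. ANCOVA estimates that slope. Unless the correlation between visits is very high, subtracting the whole baseline score adds noise.

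The trial's main efficacy comparison would therefore be less precise than its own data allow, with the same sample and the same hypothesis. The loss matters most for effects smaller than the plan's f = .175 and for coaching versus app alone, which compares only two of the three arms.

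A lesser point concerns the scales measured at all three visits. The plan gives no missing-data rule, and repeated-measures ANOVA conventionally drops a caregiver who has T3 but lacks T2. Section 14 says of participants who withdraw that "any data they have previously provided may be used in analyses", but the analysis plan does not say how partial records are handled.

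**Working it through.** **Inputs.** From section 19: N = 150, α = .05, r = .3 to .5, f = .175. From section 4: three arms with equal allocation, hence 50 per arm. Assumed: SD = 1 at each visit, complete data, and an illustrative difference of d = 0.5 SD, because the documents give no target in SD units. Paired figures below are for r = .3 / r = .5.

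**The plan's own power figure.** For the group-by-time interaction, λ = f²·N·m/(1−r), with (k−1)(m−1) and (N−k)(m−1) degrees of freedom.
- Three visits (m = 3): λ = .030625 × 450/(1−r) = 19.69 / 27.56, power .958 / .994. This is not the stated .87 to .96. That range appears at f = .15 (.873 / .963), and a sphericity correction of about 0.6 to 0.7 would also give roughly that range. The cause cannot be settled from the documents and does not affect this point.
- The between-group main effect gives only .742 / .639. The stated range is well above that, so it fits an interaction test.
- Two visits (m = 2), which is what four primary outcomes have: λ = 13.125 / 18.375, power .905 / .974.

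**Variance for a T1/T3 outcome.**
- Change score: 2(1−r) = 1.40 / 1.00.
- T3 adjusted for T1: 1−r² = .91 / .75.
- Ratio: (1+r)/2 = .65 / .75, which is 35% / 25% lower.
- Equivalent sample: 150/.65 = 231; 150/.75 = 200.

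**Three-arm test.** λ = 50·Σ(μₖ−μ̄)²/variance. For one or for both app arms shifted by d, Σ(μₖ−μ̄)² = (2/3)d², so at d = 0.5 the numerator is 50 × (2/3) × .25 = 8.33. The degrees of freedom are (2, 147) for change and (2, 146) for ANCOVA.

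| Quantity | Change score | T3 adjusted for T1 |
|---|---|---|
| λ at 0.5 SD | 5.95 / 8.33 | 9.16 / 11.11 |
| Power at 0.5 SD | .571 / .727 | .769 / .849 |
| Difference detectable with 80% power (SD) | .643 / .543 | .518 / .470 |
| Power at f = .175 | .905 / .974 | .984 / .995 |

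With two visits, f = .175 corresponds to d = f·√18 = .742 SD.

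**Coaching versus app alone.** 50 v 50, two-sided .05, SE² = variance × 2/50, d = 0.5: power .555 / .700 on change, .740 / .818 adjusted.

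**Simulation** (20,000 replicates). Type I error was .050 / .051 for both methods. With both app arms effective at 0.5 SD, power was .572 / .728 on change and .768 / .847 adjusted.

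**Other readings of the tested term.** For an unadjusted comparison at T3 the variance is 1, giving three-arm power of .727 at either correlation and .700 for the coaching comparison. At r = .3 adjustment then saves 9% of the variance, and 150 act like 150/.91 = 165. At r = .5 the figures equal the change-score ones.

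**Higher correlation.** At r = .7 and 0.5 SD, power goes from .921 on change to .957 adjusted; from an unadjusted T3 comparison it goes from .727 to .957.

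**The case against.** The strongest objection is that the largest gain depends on how an ambiguous sentence is read. The plan refers to differences at 12 weeks, which could mean a contrast at T3 within the ANOVA. On that reading, three-arm power at r = .3 rises only from .73 to .77. This stands as a limit on size: the 35% saving and the equivalent sample of 231 belong to the group-by-time reading. That reading fits the plan's stated power better, and adjustment is more powerful on either.

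Second, 0.5 SD is not in the documents, and at the plan's own f = .175 the gain is modest because power is already high. That is correct. The variance ratio, however, needs no effect size.

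Third, Aims 1 and 3 concern app usage and a mediator, neither of which is randomised, so baseline adjustment there serves to control confounding. Its absence from Aim 2 is therefore not a contradiction. That is fair. The case for adjusting Aim 2 rests on precision, not on consistency between aims.

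Fourth, the missing-data point relies on how such software usually behaves, and section 14's wording is permissive. It is separable, and no gain is quantified for the three-visit scales.

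**Conclusion.** The concern holds. For the four primary outcomes measured only at T1 and T3, adjusting T3 for T1 reduces the variance by 35% at r = .3 and 25% at r = .5 against a group-by-time test, or by 9% and 25% against an unadjusted T3 comparison. These figures assume equal variances at the two visits and complete data. The power gains at 0.5 SD also rest on that assumed effect; the gain is small at f = .175, and small against the change score at r = .7.

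The planned analysis is not invalid: with complete data the change-score comparison is unbiased under randomisation. This is an efficiency improvement that should be made, because the data are already scheduled and the cost is negligible.

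**What to change.** Before outcome data are seen, make the main Aim 2 analysis a baseline-adjusted comparison at 12 weeks.

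- **Outcomes at T1 and T3 only:** ANCOVA of T3 on arm and T1.
- **Outcomes also measured at T2:** a likelihood-based mixed model with baseline as covariate, visit-by-arm terms, and all randomised caregivers with any follow-up, so that a caregiver with T3 but no T2 is kept. State the missing-data assumption.
- **Hypothesis tested:** name it. Either keep the three-arm test, or pre-specify adjusted contrasts of each app arm against waitlist with a multiplicity rule. At 0.5 SD and α = .025 each, power is .64 / .73 adjusted against .44 / .59 on change.
- **Pooled contrast:** section 1 hypothesises that "participants who receive the FMF Connect app (with or without the additional Coaching Module) will have improve outcomes relative to the waitlist control group", which a pooled app-versus-waitlist contrast would fit. Adjusted, it gives .85 / .91 if both app arms work equally, but .32 / .38 if only one does, because the pooled difference is then 0.25 SD. That is below the .57 / .73 of the change-score three-arm test. If it is chosen, state this downside; it should not be the default.
- **Repeated-measures ANOVA:** keep as a sensitivity analysis.

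The cost is plan wording, slightly more programming and one residual degree of freedom (147 to 146). No visit, measure or participant is added.

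### Aim 2's repeated-measures ANOVA drops incomplete cases, so on the three scales collected at all three waves a missed 6-week survey discards an observed 12-week score, and no other missing-data method is given

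*Combined protocol and SAP*

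**What the plan says.** Section 19 names one method for the randomised comparison: "Repeated Measures Analysis of Variance will test whether families randomized to FMF Connect groups demonstrate improved outcomes", with the waitlist group as comparator at 12 weeks. The power statement ties that test to all three waves: "Assuming a correlation among repeated measures ranging from .3 to .5", and "with a sample of 150 and 3 time points, there will be power between .87-.96 to detect a small/medium effect ($f=.175".

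Section 14 allows gaps in the data: "Subjects can choose not to complete any or all of the study assessments". For those who withdraw completely, "any data they have previously provided may be used in analyses". The same section wants surveys even from caregivers who do not use the app. Section 10 also lets participants skip individual questions.

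The measures table in section 9 marks three outcome scales at T1, T2 and T3: "Parenting Sense of Competence Scale (3-5min)", the Reasons for Children's Behavior Scale and the Everyday Life Scale. The child behavior, family needs, knowledge and self-care measures are marked at T1 and T3 only.

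Section 5 expects some families not to complete assessments and answers by enrolling about 300 to reach 150 with usable data. Usable is not defined. No section states an analysis population, an intention-to-treat rule, a missing-data method or a sensitivity analysis.

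**The concern.** Classical repeated-measures ANOVA needs a full row of scores per person. Section 19 does not spell out deletion of incomplete cases, but that is how the named method ordinarily works, and no alternative is offered.

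Two groups are affected on the three-wave scales. A caregiver with T1 and T3 but no T2 leaves a comparison defined at 12 weeks while holding a 12-week score. A caregiver with T1 and T2 who then stops contributes nothing, although section 14 keeps those data for use. By their names, two of these scales measure parenting self-efficacy and behavior attributions, both among the six primary outcomes in section 4.

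At stake are precision, because collected answers go unused, and the randomised comparison itself, which becomes one among survey completers. If completion depends on how a caregiver is doing, and does so differently by arm, that comparison can be biased.

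**Working it through.** **1. The plan's own figure.** For the group-by-time test, λ = f²·N·m/(1−ρ), with df1 = (k−1)(m−1) and df2 = (N−k)(m−1). Section 19 and section 4 give f = .175, N = 150, m = 3 time points, k = 3 arms and α = .05.
- ρ = .3: λ = .030625 × 450/.7 = 19.69, power .958.
- ρ = .5: λ = .030625 × 450/.5 = 27.56, power .994.

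The stated range is .87 to .96, so it does not reproduce at f = .175. It does at f = .15 (.873 and .963). That mismatch is conservative and separate from this point. What matters here is that the planned test uses all three waves.

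**2. Who is dropped.** Randomisation follows baseline completion (section 9), so later gaps are at T2 or T3.

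| Pattern | Three-wave scales | T1/T3-only outcomes |
|---|---|---|
| T1 and T3, no T2 | dropped, 12-week score exists | kept |
| T1 and T2, no T3 | dropped, 6-week score exists | dropped, only baseline lost |

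**3. Retention under assumed rates.** The documents give no T2 or T3 dropout rate. Assume 15% skip T2 in every arm, and T3 is missed by 25% in each app arm and 15% on the waitlist.
- Complete three-wave cases: (2 × .75 × .85 + .85 × .85)/3 = 67%.
- T1 and T3 present: (2 × .75 + .85)/3 = 78%.

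**4. Precision, random missingness.** The simulation assumed 68 per arm (two app arms against waitlist), unit SD and a common correlation r. Deleting the 15% who skip T2 by itself inflates variance by 1/.85 = 1.18. Simulated SDs of the 12-week contrast, complete-case against likelihood:
- r = .3: .204 v .186, variance ratio (.204/.186)² = 1.20.
- r = .5: .180 v .165, ratio 1.19. A separate run gave .189 v .174, ratio 1.18.
- r = .7: .146 v .127, ratio 1.32.

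That is roughly 20% to 30%, with Monte Carlo error from 600 runs per scenario. With T1 and T3 data only, the penalty was about 4% to 6%.

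**5. Bias under different dropout mechanisms.** Values are in SD, positive favours the app; app arms are compared with waitlist.

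| What drives T3 dropout | Complete-case | Likelihood |
|---|---|---|
| Poor T1-to-T2 change, app arms only, three waves (probit slope 0.5 to 1.0) | +0.07 to +0.18 | 0.00 to about +0.02 |
| Same driver, two-wave outcome | not tabulated | about +0.03 to +0.08 |
| Same driver in every arm, three waves | about +0.03 to +0.06 | not tabulated |
| T2 level, app arms only, equal correlations | about 0 | about 0 |
| Unseen T3 value, app arms only (r = .5, slope 0.5) | +0.09 | +0.13 |
| Unseen T3 value, app arms only (r = .5, slope 1.0) | +0.16 | +0.22 |
| Unseen T3 value, same in both arms, equal completion | about 0 | about 0 |

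The first row also holds in kind with no true effect: at r = .5 and slope 0.5, complete-case shows +0.09 SD.

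**The case against.** The strongest reply is that the effect is confined and its direction is assumed.

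- **Scope.** Four of the six primary outcomes have no T2 measurement. A reader might infer that anyone missing any survey is lost from every 12-week test; the section 9 table does not support that. This stands.
- **Direction.** A reader might infer that the trial will overstate the app's benefit. The documents give no dropout rate, cause or difference by arm. They also contain counterweights: the same survey payments are set for all eligible participants (section 13), everyone is invited to follow-up whatever the arm (section 9), and non-users are wanted in the surveys (section 14). Stopping the app is not the same as stopping the surveys. This stands: bias toward the app is possible, not shown.
- **Remedy.** The mixed model does well when dropout depends on observed scores. If dropout follows unseen T3 values in the app arms, it was more biased than complete cases. This stands, and is why a sensitivity analysis belongs in the fix.
- **Power.** A reader might infer a power shortfall. Section 5 over-enrols, and the 150 may already be a count of complete cases, so none is demonstrated. Over-enrolment replaces numbers, however; it does not correct selection.
- **Inputs.** The 68 per arm equals 300 × .85 × .80/3, but the 80% is app installation, which comes after randomisation and cannot apply to the waitlist. It is only an illustrative size; the expected variance ratios and biases depend little on it.

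None of this answers the core: the only named method discards observed 12-week scores on three scales.

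**Conclusion.** The point holds in a limited form. For the Parenting Sense of Competence, Reasons for Children's Behavior and Everyday Life scales, following section 19 as written removes caregivers whose 12-week score is in hand and leaves partial data that section 14 retains unused. For child behavior, knowledge, family needs and self-care, a missed T2 removes no one and the precision gain from changing method is small.

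If 15% skip T2 and 15% to 25% miss T3 at random, complete-case variance is roughly 20% to 30% larger for three-wave outcomes and about 5% larger for two-wave outcomes. A complete-case bias of roughly 0.1 to 0.2 SD toward the app requires app-arm dropout that follows poor progress, early or unseen. It shrinks when the same mechanism acts in all arms and vanishes under some others. All these rates and mechanisms are assumptions. The documents settle neither the size nor the direction of bias, and a conclusion that the trial is biased in the app's favour would go beyond them.

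This should be changed before outcome data are compared by arm, because choosing a missing-data method afterwards invites selective analysis.

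**What to change.** In section 19, Aim 2:

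1. Replace repeated-measures ANOVA with a likelihood-based mixed model for repeated measures: arm, time, arm-by-time, unstructured covariance, and 12-week arm contrasts. State that every randomised caregiver is analysed in the assigned arm with all observed scores.
2. Report T2 and T3 survey completion by arm.
3. Add one missing-not-at-random sensitivity analysis, for example letting app-arm non-completers do worse than the model predicts. The mixed model alone does not protect against dropout driven by unseen T3 values. For two-wave outcomes it has only the baseline score to draw on.

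The cost is revised wording and slightly more analysis work, with no new data, visits or participants. The main analysis would rest on missing-at-random, which cannot be verified from the data but is weaker than the missing-completely-at-random assumption that generally justifies complete-case ANOVA.
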